3. STUDY DESIGN

Figure 5. Study Schematic

This is a randomized, double-blind, active-controlled, multicenter, parallel-group Phase 3 study of the safety and efficacy of tanezumab when administered by SC injection for up to 56 weeks in subjects with chronic low back pain. Subjects will be randomized to 1 of 3 treatment groups in a 1:1:1 ratio. Treatment groups will include:

1. Placebo SC matching tanezumab administered at an 8-week interval (total of 7 times) plus celecoxib 100 mg BID to be administered orally for 56 weeks.
2. Tanezumab 5 mg SC administered at an 8-week interval (total of 7 times) plus placebo matching celecoxib to be administered orally BID for 56 weeks.
3. Tanezumab 10 mg SC administered at an 8-week interval (total of 7 times) plus placebo matching celecoxib to be administered orally BID for 56 weeks.

The study is designed with a total duration (post-randomization) of up to 80 weeks and will consist of three periods: Screening (up to 37 days; includes a Washout Period and an Initial Pain Assessment Period [IPAP]), Double-blind Treatment (56 weeks) and Follow-up (24

weeks). The Screening Period (beginning up to 37 days prior to Randomization) includes a Washout Period (lasting 2-32 days), if required, and an IPAP (the 5 days prior to Randomization/Baseline).

Prior to entering the study, subjects must be experiencing some benefit (eg, analgesic effect) from their current stable dose regimen of oral therapy of NSAID (celecoxib 200 mg/day [100 mg BID], loxoprofen 120 to 180 mg/day or meloxicam 5 to 15 mg/day) treatment, be tolerating their NSAID regimen, be taking this medication regularly (defined as an average of at least 5 days per week) during the 30 day period prior to the Screening Visit.

At the Week 16 visit, subjects must have at least a 30% reduction in weekly average LBPI score relative to Baseline and at least a 15% reduction in weekly average LBPI score relative to Baseline at any week from Week 1 to Week 15 in order to continue investigational product. Subjects who do not meet these response criteria will be discontinued from the Treatment Period and enter the 24-week Early Termination Follow-up Period (See Section 6.9.1).

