6.4.5. Week 16 Dosing Visit

The subject will return for clinic visits at Week 16 to be assessed for efficacy and safety.

Treatment response will be calculated by the IRT. Subjects must have $\geq 30\%$ reduction in weekly average LBPI score relative to Baseline and $\geq 15\%$ reduction in weekly average LBPI score relative to Baseline at any week from Week 1 to Week 15, in order to continue investigational product. Subjects who do not meet this response criterion will be discontinued from the Treatment Period and will enter the 24 week Early Termination Follow-up (See Section [6.9](#)).

Refer to Schedule of Activities [Table 1](#) for the procedures to be performed at the Week 16 Visit.

The dosing and post-dosing procedures are the same as those as described in Section 6.4.1.2 and 6.4.1.3.

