9.1. Sample Size Determination

In terms of the study feasibility and the safety evaluation described below, the total sample size will be approximately 200 subjects (170-220 subjects, approximately 66 subjects [56-73 subjects] per treatment group). However, it is acceptable to randomize more than 220 subjects from the safety perspective as described below because primary objective is to evaluate the long-term safety.

Japanese subjects are enrolled in two studies within the tanezumab CLBP program (A4091059 and this study). In ongoing A4091059 study (randomization was finished in June 2017), 129 Japanese subjects were randomized and appropriately 57 Japanese CLBP subjects are expected to be initially randomized to the tanezumab arm. Considering approximately 133 (113-146) subjects are expected to be randomized to the tanezumab arm in this study, the safety data will be collected from approximately 190 (170-203) Japanese CLBP subjects treated with tanezumab.

The primary objective of this study is the evaluation of long term safety. The number of subjects who complete this study is estimated as described below. Both these protocols

require subjects to meet the efficacy response criteria (defined as at least a 30% reduction in weekly average LBPI score at week 16 relative to Baseline and at least a 15% reduction in weekly average LBPI score from Baseline at any week from week 1 to week 15) at week 16 in order to continue in the study. The proportion of 30% responders at week 16 was approximately 60% in two OA phase 3 studies (A4091011, A4091014) and approximately 42% in one CLBP phase 3 study (A4091012). On the other hand, the proportion of subjects discontinuing after week 16 is assumed to be approximately 10% for OA and approximately 20% for CLBP based on the results of discontinuation for reasons other than insufficient clinical response in these studies.

Therefore, the proportion of subjects expected to complete this study was calculated as approximately 54% ($=100*0.6*0.9$) based on the two OA studies and approximately 34% ($=100*0.42*0.8$) based on the CLBP study, and the proportion of completers of this study is estimated to be between 34% and 54%. Table 6 shows the relationship between the proportion of completers and the number of subjects with one year exposure.

From Table 6, if the proportion of completers is at least 43% in the CLBP program, approaching 100 subjects are expected to be treated with tanezumab for a minimum of one year.

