5.3. Methods to Manage Missing Data

Missing values in standard summaries of AEs, lab values, vital signs and ECGs will be handled per Pfizer standard algorithms.

The summary of LBPI, RMDQ, PGA and BPI-sf will use multiple imputation for missing data (where the method for imputation will be dependent on the reason for missing data). As for PGA and BPI-sf, the imputation will be used only for Week 16 and Week 56 analyses. The imputation strategies are described in the following table. While the table describes the multiple imputation strategy specific for the Week 16 time point, it also applies to Week 56 time point, eg, ‘Week 56’ would be substituted for ‘Week 16’ in the table, to describe the Week 56 multiple imputation strategy.

| Type of Missing Data | Imputation Method |
|---|---|
| Missing data resulting from discontinuation of treatment due to Death, Adverse Events (AEs) or Insufficient Clinical Response or Patient’s Meeting Protocol-Specified Pain Criteria for Discontinuation prior to or during the Week 16 visit reporting window*. | Multiple imputations will be created by sampling from a normal distribution based on the subject’s baseline score and the standard deviation (over all treatment groups) of the observed efficacy data at Week 16 overall ITT subjects. This is a multiple imputation version of BOCF single imputation method. |
| Missing data for other reasons, ie, 
 • Subject did not discontinue on or before Week 16 (includes discontinuation for any reason after the end of the Week 16 visit reporting window*), | Multiple imputations will be created by sampling from a normal distribution based on the subject’s last score and the standard deviation (over all treatment groups) of the observed efficacy data at Week 16 over all ITT subjects. For example if last observation |

| | |
|---|---|
| 
 • Subject discontinued for a different reason prior to or during the Week 16 visit reporting window*. | 
for a subject is at Week 12, then the imputation sample for that subject is created using the subject’s Week 12 observation and the standard deviation of the Week 16 observations for all subjects. Note: a subject’s last observation may be the Baseline observation. This is a multiple imputation version of LOCF single imputation method.
 |
|---|---|

* See [Appendix 2.1](#) for a definition of the reporting windows.

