6.2.6. Euro Quality of Life Health State Profile (EQ-5D-5L™)

EQ-5D-5L™ dimensions and overall health utility score at Baseline, Weeks 16 and 56

The Baseline and Weeks 16 and 56 responses in the five dimensions (mobility; self-care; usual activity; pain/discomfort; anxiety/depression) and overall health utility score from the EuroQol 5 Dimensions (EQ-5D-5L) will be summarized by treatment group. This summary will use observed data only (no imputation for missing data). The calculation of the overall health utility score is described in [Appendix 2.3](#).

An additional question, called the EQ-VAS asks the patient to rate their health today using a VAS scale from 0 (the worst health you can imagine) to 100 (the best health you can imagine). This will be summarized along with the health utility score.

A table showing number and percentage of subjects will summarize the response for each dimension (item) of the EQ-5D-5L at each timepoint. These summary tables will be shown by treatment group. In addition, for each treatment and each time point assessed, descriptive statistics (mean, standard deviation, median, minimum, maximum, number of subjects) will be shown for the health utility score, and the EQ-VAS measure of health today.

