6.2.7. Work Productivity and Activity Impairment Questionnaire: Low Back Pain (WPAI:LBP)

WPAI:LBP change from Baseline to Week 16, 56 and 64, in the percent work time missed due to chronic low back pain, percent impairment while working due to chronic low back pain, percent overall work impairment due to chronic low back pain, and percent activity impairment due to chronic low back pain.

This summary of WPAI:LBP will use observed data only (no imputation for missing data). These are listed below:

- Percent work time missed due to Low Back Pain.
- Percent impairment while working due to Low Back Pain.
- Percent overall work impairment due to Low Back Pain.
- Percent activity impairment due to Low Back Pain.

The calculation of these endpoints is described in [Appendix 2.3](#). The change from Baseline in the impairment scores of the WPAI:LBP will be summarized by treatment group.

The summary will show number and percentage of patients with a decrease, no change, and an increase in score for the change from Baseline to each timepoint. In addition, descriptive statistics (mean, standard deviation, median, min, max, number of subjects) for the change from Baseline to each timepoint and the absolute scores at the individual timepoints of Baseline and Weeks 16, 56, and 64 will be calculated.

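### Post-Week 16 observed-only summaries of EQ-5D-5L, WPAI:LBP and the intermediate PGA-LBP and BPI-sf means carry an ITT label but contain only subjects who met the Week 16 response criteria

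*SAP*

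**What the plan says.** Protocol Section 3 sets the continuation rule: "At the Week 16 visit, subjects must have at least a 30% reduction in weekly average LBPI score relative to Baseline", together with a 15% reduction at some week from 1 to 15. The consequence is that "Subjects who do not meet these response criteria will be discontinued from the Treatment Period". Protocol 6.4.5 repeats this for the Week 16 dosing visit.

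For EQ-5D-5L, SAP 6.2.6 states "This summary will use observed data only (no imputation for missing data". For WPAI:LBP, SAP 6.2.7 states "This summary of WPAI:LBP will use observed data only (no imputation for missing data". For the other two instruments, SAP 5.3 states "As for PGA and BPI-sf, the imputation will be used only for Week 16 and Week 56 analyses". Appendix 1 agrees. It has no imputed row for EQ-5D-5L, EQ-VAS or WPAI:LBP, and only observed-data rows for the PGA-LBP means at Weeks 24, 32, 40 and 48 and the BPI-sf means at Weeks 24 and 40. Every row is marked ITT.

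SAP 6.2 excludes treatment-period efficacy data from any window more than 8 weeks after the last SC dose window.

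**The concern.** SAP 5.3 gives a clear reason for imputing: leaving treatment because of death, an adverse event or lack of efficacy is a bad result and should be scored as one. The SAP follows this for LBPI and RMDQ at every analysis week to Week 56, for PGA-LBP and BPI-sf means at Weeks 16 and 56, and for PGA-LBP response at Weeks 24 and 40. It does not follow it for the summaries listed above. There, subjects removed for insufficient pain response simply disappear.

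The result is an ITT-labelled table that starts from everyone at Baseline and ends with selected responders. EQ-5D-5L is tabulated as values at each visit, so its apparent gain arises when an all-ITT Baseline is read against a responder-only Week 56. WPAI:LBP, PGA-LBP and BPI-sf are summarised as change, so the change itself is computed in the selected subjects. A PGA-LBP mean and a PGA-LBP response rate at the same week would also describe different populations.

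**Working it through.** **1. The plan's own attrition figures (Protocol 9.1).** "The proportion of 30% responders at week 16 was approximately 60% in two OA phase 3 studies" and "approximately 42% in one CLBP phase 3 study (A4091012"). Later discontinuation is taken as 10% and 20%.
- OA basis: 0.60 × 0.90 = 0.54, stated as 54%.
- CLBP basis: 0.42 × 0.80 = 0.336, stated as 34%.

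Both figures reproduce. At about 66 per arm, 0.42 × 66 = 27.7 to 0.60 × 66 = 39.6 subjects meet the 30% criterion, and 0.336 × 66 = 22.2 to 0.54 × 66 = 35.6 complete. So 40-58% of an arm is lost on that criterion alone.

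**2. Where data from a subject who fails the criteria can land.** No Week 16 dose is given, so the last SC dose is Week 8 (Day 57 ± 7). Early Termination Visit 1 is 8 weeks later and Visit 2 is 16 weeks later, each ± 7 days.
- Visit 1: nominal Day 57 + 56 = 113; latest 57 + 7 + 56 + 7 = 127.
- Visit 2: nominal Day 57 + 112 = 169; latest 57 + 7 + 112 + 7 = 183.

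The relevant rules are in SAP 6.2 and Appendix 2.1:
- EQ-5D-5L (collected at Visit 1) and WPAI:LBP (Visits 1 and 2): the Week 16 window is Days 2-253 and the Week 56 window opens on Day 254. Even Day 183 falls in Week 16.
- PGA-LBP and BPI-sf: nominal Visit 2 (Day 169) and its latest day (183) fall in the Week 24 window (Days 142-197 and 142-225 respectively). With the last dose in the Week 8 window, Week 16 is the last on-treatment window, so the Week 24 record is excluded.

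These subjects therefore contribute to none of the summaries at issue.

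**3. Who does contribute.** Only subjects who met the Week 16 criteria, but not only completers. Because the Week 56 window for EQ-5D-5L and WPAI:LBP opens on Day 254, someone last dosed at Week 32 (Day 225) has Visit 1 on Day 225 + 56 = 281, which falls inside it.

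**4. Illustration for change scores.** Let a share P be observed with mean change m, and give zero change to everyone else. The all-subject mean is P × m, so the ratio of observed to all-subject mean is 1/P.
- Week 56, completers only: 1/0.54 = 1.85 to 1/0.336 = 2.98.
- Just after Week 16: 1/0.60 = 1.67 to 1/0.42 = 2.38.

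**5. Illustration of selection, with assumed correlation.** Suppose an endpoint has correlation ρ with pain reduction under a normal model. The mean among those passing exceeds the all-subject mean by ρ × φ(c)/P standard deviations, with c = z(1 − P). For P = 0.42 this is 0.93ρ; for P = 0.60 it is 0.64ρ. With ρ assumed to be 0.3-0.7, the shifts are 0.28-0.65 SD and 0.19-0.45 SD.

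If two arms had pass rates of 42% and 60% (figures from different studies, not arm-specific forecasts), a true difference of 0.14-0.32 SD would shrink to 0.05-0.12 SD among those passing. Selection of this kind tends to compress arm differences rather than create them.

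**The case against.** The best defence is that these are descriptive secondary summaries and the SAP follows the protocol. Protocol 9.3 specifies observed data for efficacy and leaves missing-data sensitivity work optional. No hypotheses are tested (SAP 5.1). Differential retention has its own analysis: discontinuation for insufficient response or the protocol pain criteria is compared with celecoxib with 95% CIs and Kaplan-Meier curves (SAP 6.2.8). The tables show the number of subjects. PGA-LBP and BPI-sf means have multiple imputation, BOCF and LOCF at Weeks 16 and 56, and PGA-LBP response has BOCF, LOCF and mixed versions at Weeks 24 and 40. WPAI work items are also missing by design for people not in work, so blanket imputation would be wrong.

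All of this is correct, and it limits the point to EQ-5D-5L and WPAI:LBP at Week 56 and the intermediate PGA-LBP and BPI-sf means. It does not remove it. A falling n does not tell the reader that the missing subjects are mainly those who failed a pain criterion, and nothing provides Baseline for those who remain. SAP 5.3 promises missing-data sensitivity analyses but describes none for EQ-5D-5L or WPAI:LBP.

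A reader might go further and infer that the SAP plans arm comparisons conditioned on response. It does not: SAP 5.2.2 attaches differences in means only to the LBPI and RMDQ ANCOVA, which uses multiple imputation at all weeks to 56. The conditioning matters when by-arm tables are read side by side, and for the PGA-LBP and BPI-sf differences with 95% CIs that Protocol 9.3 still promises. Nor do the documents support saying that a treatment keeping more subjects in response would show no advantage, since SAP 6.2.8 reports that advantage separately.

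**Conclusion.** The point holds within those limits. The listed summaries carry an ITT label but describe subjects who met the Week 16 response criteria, expected to be about 42-60% of those randomized, with 34-54% completing. The exclusion follows from the visit schedule and windows and needs no assumption beyond adherence to them. Upward bias of the apparent gain additionally assumes that these scores improve with pain.

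The documents give no SD or correlation for these instruments, so the bias cannot be sized. The 1.9-3.0 ratio should not be taken as an estimate of it. It assumes that only completers are observed at Week 56 and that everyone else has zero change; it can describe a change score such as WPAI but not EQ-5D utility or EQ-VAS values; and it is not what the fix below would return, because subjects leaving for other reasons would receive a last-value-based score. As these are descriptive secondary endpoints, the matter is one of correct description and consistency with SAP 5.3, worth correcting but not a threat to the primary safety objective.

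**What to change.** In SAP 5.3, 6.2.6, 6.2.7 and Appendix 1, add an imputed summary alongside each observed one, using the SAP's existing reason-based rules: Baseline-based for failure of the Week 16 criteria, lack of efficacy, adverse event or death, and last-value-based otherwise. Either the SAP 5.3 multiple imputation or its mixed BOCF/LOCF form would serve. The mixed form is currently defined only for response endpoints, so its use for means would need a sentence. Apply it to:
- EQ-5D utility, EQ-VAS and WPAI:LBP at Week 56, with WPAI work items imputed only among those employed so that not-applicable items are left alone;
- PGA-LBP means at Weeks 24, 32, 40 and 48;
- BPI-sf means at Weeks 24 and 40 (it is not collected at Weeks 32 or 48).

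Retitle the observed tables *subjects continuing on treatment after the Week 16 response criteria*, and show n and Baseline for those same subjects.

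The cost is SAP wording and a few extra tables, with no new data collection. Stated gains would become smaller, and if the mixed BOCF/LOCF form is chosen it brings the usual limits of single imputation.

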6.2.7. Work Productivity and Activity Impairment Questionnaire: Low Back Pain (WPAI:LBP)

WPAI:LBP change from Baseline to Week 16, 56 and 64, in the percent work time missed due to chronic low back pain, percent impairment while working due to chronic low back pain, percent overall work impairment due to chronic low back pain, and percent activity impairment due to chronic low back pain.

This summary of WPAI:LBP will use observed data only (no imputation for missing data). These are listed below:

- Percent work time missed due to Low Back Pain.
- Percent impairment while working due to Low Back Pain.
- Percent overall work impairment due to Low Back Pain.
- Percent activity impairment due to Low Back Pain.

The calculation of these endpoints is described in [Appendix 2.3](#). The change from Baseline in the impairment scores of the WPAI:LBP will be summarized by treatment group.

The summary will show number and percentage of patients with a decrease, no change, and an increase in score for the change from Baseline to each timepoint. In addition, descriptive statistics (mean, standard deviation, median, min, max, number of subjects) for the change from Baseline to each timepoint and the absolute scores at the individual timepoints of Baseline and Weeks 16, 56, and 64 will be calculated.

6.2.8. Discontinuation Due to Lack of Efficacy

Incidence of and time to discontinuation due to lack of efficacy

The incidence of discontinuation from treatment due to ‘INSUFFICIENT CLINICAL RESPONSE’ and ‘PATIENT MEETS PROTOCOL-SPECIFIED PAIN CRITERIA FOR DISCONTINUATION’ on the End of Treatment Subject Summary Case Report Form will be summarized along with 95% CIs using incidence up to the end of treatment period (the Week 56 visit or early termination). Discontinuation in the post-treatment safety follow-up period will not be included in this endpoint for analysis, but will be summarized as part of the safety tables. The differences with 95% CIs will be calculated for the comparisons of each

tanezumab group versus the celecoxib group. A supplementary analysis for the incidence of discontinuation from treatment due to 'INSUFFICIENT CLINICAL RESPONSE' will also be performed.

The time to discontinuation due to lack of efficacy will be summarized and estimated failure curves will be produced using Kaplan-Meier estimation. The time to selected percentiles will also be shown. These are influenced by the frequency of discontinuation, but are expected to be shown for the 1st, 2nd, 5th, 10th and 25th percentiles, in addition to the minimum and maximum time to discontinuation. Any subject who discontinues for any other reason prior to the planned Week 56 visit will be censored at the time of discontinuation. Subjects who complete the study or who discontinue for any reason after the Week 56 visit (including lack of efficacy) will be censored at the Week 56 visit.

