5.2.4. Analyses for Time to Event Data

Survival curve estimates (time to 1st, 2nd, 5th, 10th and 25th percentiles, and minimum and maximum values) and a plot of the time to event will be shown using the Kaplan-Meier estimates. Only discontinuation up to the end of treatment period (Week 56 visit or early discontinuation) will be used in this analysis.

Any subject who discontinues for any other reason than lack of efficacy prior to the Week 56 visit uses censoring at the time of discontinuation. Imputation of time to event for completed subjects or discontinued subjects (for any reason) after the Week 56 visit uses censoring at the Week 56 visit time point.

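### The Kaplan-Meier failure curve for lack-of-efficacy discontinuation censors all other discontinuations, so it can overstate the cumulative probability; the crude incidence and its difference versus celecoxib are unaffected

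*SAP*

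**What the plan says.** SAP 6.2.8 defines the event as stopping treatment for either of two recorded reasons: insufficient clinical response, or meeting the protocol's pain criteria for discontinuation. It plans two kinds of output.

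- **Crude incidence.** The incidence "will be summarized along with 95% CIs using incidence up to the end of treatment period". For the contrast with control, "The differences with 95% CIs will be calculated for the comparisons of each" tanezumab group against celecoxib.
- **Timing.** Here "estimated failure curves will be produced using Kaplan-Meier estimation", and times are "expected to be shown for the 1st, 2nd, 5th, 10th and 25th percentiles". The censoring rule is "Any subject who discontinues for any other reason prior to the planned Week 56 visit will be censored at the time of discontinuation".

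SAP 5.2.4 gives the same rule in the general methods: "Any subject who discontinues for any other reason than lack of efficacy prior to the Week 56 visit uses censoring at the time of discontinuation". Subjects who complete treatment are censored at the Week 56 visit. Appendix 1 lists Kaplan-Meier estimates as the only method for the time-to-event endpoint, and Protocol 9.3 also names Kaplan-Meier with the same percentiles. Neither document mentions a cumulative incidence function or any other competing-risk method.

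SAP 6.2.8 also closes the endpoint when treatment ends: "Discontinuation in the post-treatment safety follow-up period will not be included in this endpoint for analysis".

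**The concern.** Kaplan-Meier treats a censored subject as someone who could still have the event later, at the same rate as those still under observation. That does not fit here. A subject who has stopped treatment for an adverse event or another reason cannot afterwards stop treatment for lack of efficacy, and the SAP counts nothing after treatment ends. One minus Kaplan-Meier therefore describes a setting in which nobody stops for any other reason. It is not the proportion of treated subjects expected to stop for lack of efficacy.

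The design makes this visible. Lack-of-efficacy stops should concentrate at the Week 16 response rule (Protocol 3 and 6.4.5). Each subject censored before Week 16 leaves the denominator just ahead of the largest step in the curve.

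What is at stake is consistency and reading. SAP 6.2.8 could report two different figures for what looks like the same quantity at Week 56, a crude incidence and a higher value read from the curve. Within that section the curve is also the only output that shows a Week 16 probability.

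**Working it through.** **Inputs from Protocol 9.1.** The share of 30% responders at Week 16 is about 60% in two osteoarthritis studies and about 42% in one chronic low back pain study. Discontinuation after Week 16 for reasons other than insufficient response is about 10% and 20% respectively.

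**Reproducing the plan's own figure.** Expected completers are the responder share times one minus later dropout:
- osteoarthritis inputs: 0.60 × 0.90 = 0.540, stated as 54%;
- low back pain inputs: 0.42 × 0.80 = 0.336, stated as 34%.

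Both reproduce. The documents give no expected value for the failure curve or its percentiles.

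**Assumed inputs, shown as ranges because the documents do not give them.** Other-reason stops before Week 16, *q*: 0–20% of subjects. Lack-of-efficacy stops before Week 16: 0–5% of subjects. Lack-of-efficacy stops after Week 16: 0–10% of those continuing. The Week 16 failure share *p* is 1 − 0.42 = 0.58 or 1 − 0.60 = 0.40, applied to subjects still on treatment at Week 16.

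**Simplest case: all lack-of-efficacy stops at Week 16.**
- Kaplan-Meier failure = *p*, because the *q* have left the risk set.
- Cumulative incidence = (1 − *q*) × *p*.

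| *q* (assumed) | 1 − KM, *p* = 0.58 | Cumulative incidence | 1 − KM, *p* = 0.40 | Cumulative incidence |
|---|---|---|---|---|
| 0% | 58.0% | 58.0% | 40.0% | 40.0% |
| 5% | 58.0% | 0.95 × 0.58 = 55.1% | 40.0% | 0.95 × 0.40 = 38.0% |
| 10% | 58.0% | 0.90 × 0.58 = 52.2% | 40.0% | 0.90 × 0.40 = 36.0% |
| 20% | 58.0% | 0.80 × 0.58 = 46.4% | 40.0% | 0.80 × 0.40 = 32.0% |

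**Full grid.** A weekly two-cause model over Weeks 1–56, covering all the ranges above, gives an excess of 1 − KM at Week 56 of 0 to 13 points with the low back pain inputs and 0 to 10 points with the osteoarthritis inputs. With no early other-reason stops, the protocol's 10–20% later dropout adds only 0 to 0.5 points, because few lack-of-efficacy events remain after Week 16.

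**Percentile times.** At the Protocol 9.1 rates, the times to the 1st, 2nd, 10th and 25th percentiles are the same to the week under both methods. The 5th moves at most from Week 15 to Week 14. Larger shifts need a much lower Week 16 failure share. For example, with an assumed 20% failing at Week 16 and 5% early other-reason stops, the 25th percentile falls at about Week 41 under Kaplan-Meier against about Week 55 for the cumulative incidence. In no scenario is the Kaplan-Meier time later.

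**Crude incidence.** Every treated subject either reaches the Week 56 visit or has a recorded discontinuation. The crude proportion to end of treatment is therefore the cumulative incidence at Week 56, and the censoring rule does not touch it.

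**The case against.** The strongest reply is that the two estimators answer different questions. Kaplan-Meier with other stops censored describes failure among subjects who have not left for another reason. If failure at Week 16 among those still treated were equal in two arms, the cumulative incidence would make the arm with more other-reason dropout look better on lack of efficacy. The SAP states its censoring rule openly, tests no hypotheses (SAP 5.1), and gives the probability separately as a crude incidence. SAP 6.5.2 also plans discontinuation counts by treatment group, reason and study-week band; cumulated over the number treated, these approximate the cumulative incidence. All of this stands, and it keeps the point small. It does not justify an unlabelled failure curve that may disagree with the crude incidence reported beside it.

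Three stronger readings are tempting, and the documents do not support them.

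- A reader might infer that the comparison with celecoxib is distorted. The only planned contrast on this endpoint is the difference in crude incidence; no log-rank test, hazard ratio or Kaplan-Meier difference is planned. Comparing the curves by eye could mislead only if early other-reason stops differ by arm. The documents do not establish that: Protocol 1.2.4.2 reports similar withdrawal for adverse events on tanezumab monotherapy 5–10 mg and active comparator in osteoarthritis.
- A reader might infer that the percentiles are overstated. They are times, so a curve that is too high makes them earlier or leaves them unchanged.
- A reader might infer that everyone censored early is counted as failing at Week 16. Their weight is shared among all still at risk, including those who pass. If 10% are censored and 50% of all subjects fail, Kaplan-Meier gives 0.50 / 0.90 = 55.6%, a rise of 5.6 points and not 10.

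**Conclusion.** The concern holds in a narrow form. The planned curve overstates the cumulative probability of stopping for lack of efficacy whenever other-reason stops precede lack-of-efficacy stops, and it can bring percentile times forward. With the low back pain inputs and all events at Week 16, the excess is 58.0 − 55.1 = 2.9 points for 5% early other-reason stops, 5.8 points for 10% and 11.6 points for 20%. It is zero if there are none. Percentile times barely move at the protocol's rates.

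The size rests on the rate of other-reason stops before Week 16, which the documents do not give, and on applying the earlier trials' non-responder share to subjects still on treatment at Week 16. The direction rests on neither.

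The effect is confined to a descriptive curve and percentile times for a secondary endpoint. The crude incidence, its difference versus celecoxib and the primary safety analyses are untouched. It is worth correcting because the correction is easy, but no planned comparison depends on it.

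**What to change.** In SAP 5.2.4, 6.2.8 and the matching row of Appendix 1, replace the Kaplan-Meier failure curve and percentiles with the Aalen-Johansen cumulative incidence function by treatment group. Treat discontinuation for any other reason as the competing event and censor only at the Week 56 visit. Take the percentile times from that function, and report a percentile as not reached where the curve stays below it. Use the same event definition and denominator as the crude incidence, so that the two agree at Week 56. Read at Week 16, the function also gives a figure for the earlier of the two time points named in Protocol 9.3. Keep the crude incidence and its difference versus celecoxib as planned.

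Protocol 9.3 names Kaplan-Meier, so record the change as a departure from it. Protocol 9 and SAP 2 allow the SAP to modify planned methods and require an amendment only for major changes to the primary endpoint or its analysis, which this is not. If Kaplan-Meier is kept as a supplement, label it as conditional on no other discontinuation.

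The cost is SAP wording in three places and a standard software option, with no new data.
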